Study Personnel Training. Prior to initiation of participant enrollment (and annually thereafter), all project personnel will undergo project specific human subjects training that addresses risks to subjects; protection against risks; potential benefits of research to subjects and others; and the importance of knowledge to be gained. Additionally, all study personnel will be required to

complete training in the Responsible Conduct of Research every three years. This includes online CITI training in responsible conduct of research, good clinical practice, and human research protections.

Participant Screening. Potential research participants will undergo a baseline evaluation to ensure they meet eligibility criteria, and it is safe for them to participate. Adverse events will be minimized by identifying and excluding patients at high risk during the screening process (described in section 5.4 Inclusion/Exclusion criteria).

Intervention. Participants will be monitored for side effects and adverse events during all study intervention sessions. The RAMP intervention is considered an introductory program and has been designed to minimize risks and meet the needs and skill level of participants. RAMP integrates mindfulness practices, pain education, pain-specific exercises, and cognitive and behavioral strategies. Based on our previous studies and the existing literature, we believe RAMP to be minimal risk. It is expected that some participants may experience limited and short-lasting physical and/or mental agitation. All participants will be provided health contact information as part of the study materials (e.g., workbook, website). Contact information will include the national Veterans Crisis Line (dial 988 and press 1) and local VA Healthcare System contacts.

Intervention facilitators (health coaches) will be trained by investigators and monitored for fidelity to ensure they are implementing the interventions in a manner that optimizes patient safety. This will include how to monitor for potential emotional or physical discomfort during session activities and how to implement safety procedures if needed.

Project Personnel Support. All participants will have access to the telephone support line and email address, staffed by trained team members, who will provide technical assistance and be able to answer basic questions related to intervention. We will continually update our procedures and manual of operations to reflect commonly asked questions.

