5.1.2 Feasibility/Pilot and RCT

Interventions

RAMP (UG3/Phase 1 Aim 2 and UH3/Phase 2 Aim 1)

Eligible participants will be enrolled in the RAMP intervention group and mailed (by

Abbreviated title: Rural Veterans Applying Mind Body Skill for Pain (RAMP)

Version date: 8/22/25

postal mail) tailored informational materials, including an introductory letter, copy of the information sheet, schedule with meeting dates/times, a workbook, and directions for accessing the intervention materials online. In keeping with our pragmatic approach, participants will not be asked to limit any other treatment. RAMP will take place over a 3-month period, delivered virtually via a VA-approved program (e.g., Microsoft Teams, Webex). For the UG3/Phase 1, the first session was a one-to-one session (60 minutes) with a health coach to complete a Personal Health Plan. This was followed by 11 weekly group sessions (90 minutes each) facilitated by the health coach. For the UH3/Phase 2, revisions were made, and all 9 weekly sessions will be held as a group (90 minutes each) facilitated by the health coach. Videos will be interspersed with workbook reflections and group discussions facilitated by the health coach. In session, group viewing of expert narrated videos will provide consistent education and training in content (e.g., pain education, mind-body skill training like mindfulness, physical movement, wellbeing). A range of customizable options and resources will be provided to meet Veterans' preferences, needs, and abilities. Email, SMS (using Qualtrics FedRAMP), and/or phone communication will provide reminders of sessions ahead of time. Participants will be asked to remain in close contact with health coaches and let them know of any need to miss a session. Study staff will follow-up with participants who do not attend session(s). Additional contact reasons, particularly towards the end of the study, may include alerting participants to study results and other research participation opportunities.

Usual Care (UH3/Phase 2 Aim 1 only)

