Participants randomized to the Usual Care (UC) condition will not be asked to do anything besides complete the follow-up surveys. In keeping with our pragmatic approach, patients will not be asked to limit any other treatment. They will be mailed (by postal mail) an introductory letter, copy of the information sheet, and schedule of when they will be contacted to complete the follow-up surveys. After completing the final follow-up survey, they will be mailed information about how to access the intervention materials online.

Follow-up

Participants will be asked to complete follow-up surveys online at 3 months (UG3/Phase 1 and UH3/Phase 2) and 6 months (UH3/Phase 2 only) after the intervention period began. Survey invitations will be sent via email and SMS (using Qualtrics FedRAMP). Reminders will be sent to non-responders, including phone and mail follow-up if necessary.

All recruitment and follow-up activities will be performed by project staff at the Minneapolis VA.

Participant Population Characteristics

In order to qualify for the US Military, and eventually become a Veteran, individuals must be at least 18 years old. Since children (less than 18 years of age) do not exist in the population of interest, they will not be included in the study. This is also consistent with NIH Policy and Guidelines on the Inclusion of Children as Participants in Research Involving Human Subjects.

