5.2 Research Participants Expected Risks

The potential risks are considered minimal for research participants in both the active and control groups. These include risks associated with the following:

- **Completing Health Surveys.** Participants will be asked to complete health surveys as part of the screening and follow up data collection. The nature of the questions might be distressing to some individuals.
- **Breach of Confidentiality.** There is a very small risk of breach of confidentiality and privacy. New information will be gathered from participants and is not anticipated to place individuals at risk of criminal or civil liability or be damaging to the participants' financial standing, employability, educational advancement, or reputation.

The fluctuations associated with the natural history of pain and mental health conditions that co-occur with pain may be associated with some risk.

- **Natural History of Pain.** People with pain that is chronic in nature often experience fluctuations in pain severity, location, character, and quality unrelated to study participation (e.g., aggravated by lifting at work or home).
- **Natural History of Mental Health Conditions in People with Pain:** People with chronic pain often experience fluctuations in their levels of distress or aggravation of mental health conditions unrelated to study participation (e.g., stressful life events).

Additional Risk Associated with RAMP Program (active intervention).

The additional potential risks associated with the RAMP Program are considered minimal. All Veteran patients in the VA health system have a primary health care provider; they will not be asked to limit any other treatment they might be receiving for their pain. Participants will be asked to take part in a group behavioral intervention via a VA-approved videoconferencing program (for example, Webex). Minimal risks associated with the experimental educational intervention may occur in program sessions and practicing on one's own. The intervention is not physically invasive, embarrassing, or offensive, and not expected to have adverse lasting impact. Expected risks include:

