- Experiencing some anxiety or nervousness when participating in group activities (e.g., discussions); mild short-lasting physical discomfort (e.g., muscle and joint soreness) as a result of performing short periods of exercises (~5-10 minutes); and feeling emotional when doing the brief mind-body practices (~5-10 minutes), which include mindfulness and behavioral coping strategies (e.g., relaxed breathing, guided imagery, progressive muscle relaxation).

Additional Risk Associated with Usual Care (control group, UH3/Phase II only).

The additional potential risks associated with being randomly assigned to Usual Care are considered minimal. As noted previously, all Veteran patients in the VA health system have a primary health care provider. Participants in the Usual Care condition will be instructed to do what they normally would, on their own. Patients will not be asked to limit any other treatment they might be receiving for their pain. After completing the final follow-up survey, they will be mailed information about how to access the intervention materials online, which they can use on their own if they wish.

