Intervention	
• The RAMP intervention has been designed to include activities and exercises that are suitable for a range of abilities and preferences. The mind-body skill practices are short in duration (~5-10 minutes), lowering the risk of emotional discomfort or psychological events.• Participants will also be given the option to refrain from participating in activities that feel uncomfortable.• Facilitators will be trained and supervised by the clinical psychologist MPI, chiropractic MPI, and Co-Is with clinical pain management experience to actively monitor for potential emotional or physical distress during session activities and how to implement safety procedures. The manual of operations details steps for assessing the nature of the situation, responding appropriately to ensure participant safety, documenting the event and notifying the Project Director and the MPIs (see Section 6).• Participants in which imminent risk for suicidality is possible will be offered a warm hand off to the Veterans Crisis Line; if they decline, or disconnect, staff will immediately 1) contact the local police department to conduct a wellness check, then 2) contact the Veterans Crisis line to report event and 3) contact the participants' local suicide prevention team.

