---------------------	----------------------------------------------------------------------------------------------------------------------------------------------------------------------------------------------------------------------------------------------------------------------------------------------------------------------------------------------------------------------------------------------------------------------------------------------------------------------------------------------------------------------------------------------------------------------------------------------------------------------------------------------------------------------------------------------------------------------------------------------------------------------------------------------------------------------------------------------------------------------------------------------------------------------------------------------------------------------------------------------------------------------------------------------------------------------------------------------------------------------------------------------------------------------------------------------------------------------------------------------------------------------------------------------------------------------------------------------------------------------------------------

6 Adverse Event/ Unanticipated Problems

All project team members will undergo project-specific human subjects training that addresses risks to subjects; protection against risks; potential benefits of research to subjects and others; and the importance of knowledge to be gained. Additionally, all study personnel will be required to complete training in the Responsible Conduct of Research every three years. This includes online CITI training in responsible conduct of research, good clinical practice, and human research protections. Current human subjects training records are regularly updated by the Minneapolis VA IRB and checked annually at Continuing Review.

All project team members will be trained in study specific protocols relevant to their role, including detailed safety procedures to mitigate risk to participants (see Section 5 and Table 1 above). We will use active and passive monitoring of adverse events and unanticipated problems in the study. Serious or possibly related adverse events and unanticipated problems can be learned about in the following ways:

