- From participants, who will be encouraged to contact the Project Director or an MPI
- From direct queries in the self-report surveys
- From observations by project staff during baseline screening calls, interventions, and other interactions with participants

Participants who experience possibly related serious adverse events and unanticipated problems will be contacted by the Project Director or delegate to gather information for adverse event reporting (see Section 6.1 below) and ensure safety procedures are followed (see Section 5 above).

Events identified as serious adverse events or unanticipated problems will be adjudicated by the MPIs and Co-Is for: confirmation of severity, relatedness and expectedness based on the definitions below.

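### Session monitoring gives RAMP an extra scheduled route for detecting non-serious adverse events, and no split of the by-group counts by source is written

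*Combined protocol and SAP*

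**What the plan says.** **Detection in RAMP.** Protocol section 3.3.3 says: "Participants will be monitored for side effects and adverse events during all study intervention sessions". The Schedule of Activities (section 2.3, Table 3) marks adverse events at the intervention sessions as well as at 3 and 6 months. Section 5.1.2 sets the number for the randomized trial: "all 9 weekly sessions will be held as a group (90 minutes each) facilitated by the health coach". DSMP 5.2.1, Table 1, has facilitators trained "to actively monitor for potential emotional or physical distress during session activities and how to implement safety procedures".

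**Detection in Usual Care.** Section 5.1.2: "Participants randomized to the Usual Care (UC) condition will not be asked to do anything besides complete the follow-up surveys".

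**Shared by both arms.** Under section 3.3.3 the surveys carry a symptom checklist, an item-by-item question on relatedness, and separate questions on hospital stay, disability and life-threatening events. All participants are also encouraged to contact the staff about side effects.

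**Use of the events.** DSMP 6.2 has the team record every adverse event it becomes aware of. DSMP 7.5 presents the closed report by group, and its safety summary covers counts and rates of adverse events alongside serious events and unanticipated problems. Neither section mentions the source of an event. Section 5.8 does not mention adverse events at all.

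**Two kinds of event.** DSMP 5.2 lists as a RAMP risk "mild short-lasting physical discomfort (e.g., muscle and joint soreness) as a result of performing short periods of exercises". It also says of all participants: "People with pain that is chronic in nature often experience fluctuations in pain severity, location, character, and quality unrelated to study participation".

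**The concern.** The two arms are not observed in the same way for mild events. A sore back or a low mood in week 4 can reach the record through a session in RAMP. In Usual Care it reaches the record only if the participant contacts the staff or ticks it later on a survey.

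If all sources are pooled and tabulated by arm, a RAMP excess has two possible explanations that the table cannot separate: the program causes short-lived reactions, or the same background symptoms are noticed more often. The mistake can go either way. The monitoring board could read extra detection as harm, or dismiss a real session reaction as the result of more contact.

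**Working it through.** The plan gives no adverse event rate, capture rate or event timing, so it has no figure of its own to reproduce here. The check has two parts.

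**1. Routes side by side**

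| Route | RAMP | Usual Care |
|---|---|---|
| Monitoring at nine weekly sessions (2.3, 3.3.3, 5.1.2, DSMP Table 1) | yes | no |
| Checklist at 3 and 6 months (2.3, 3.3.3) | yes | yes |
| Spontaneous report (3.3.3) | yes | yes |

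The difference is one scheduled route, present in one arm only. The follow-up of missed sessions in 5.1.2 is not counted, because that text does not mention adverse events.

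**2. Size of the detection effect, under assumptions**

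Suppose the true event rate is the same in both arms. Let

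- p = share of events captured by the surveys, assumed 0.7;
- s = share of events during the program captured at sessions with full attendance, assumed 0.1, 0.3 or 0.5;
- a = attendance, from 6/9 (the adherence threshold in DSMP 7.1.2) to 1;
- f = share of events that fall in the nine program weeks: 9/26 = 0.346 if spread evenly over six months, 1 if all fall there.

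Assume also that session and survey capture are independent and that each event is counted once. Usual Care records p. RAMP records p + (1 − p) × f × s × a. The ratio is

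1 + f × s × a × (1 − p)/p, with (1 − p)/p = 0.3/0.7 = 0.429.

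| s | a | f = 0.346 | f = 1 |
|---|---|---|---|
| 0.1 | 6/9 | 1.010 | 1.029 |
| 0.1 | 1 | 1.015 | 1.043 |
| 0.3 | 6/9 | 1.030 | 1.086 |
| 0.3 | 1 | 1.045 | 1.129 |
| 0.5 | 6/9 | 1.049 | 1.143 |
| 0.5 | 1 | 1.074 | 1.214 |

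If half of the participants have a true event (also an assumption), Usual Care shows 0.5 × 0.7 = 35.0%.

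- Even spread: RAMP shows 35.0% × 1.0099 = 35.3% up to 35.0% × 1.0742 = 37.6%.
- All events in the nine weeks: 36.0% to 42.5%.

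With 250 per arm (500/2), the standard error of 37.6% − 35.0% is √(0.35 × 0.65/250 + 0.376 × 0.624/250) = 4.3 points. The largest even-spread artefact is 2.6/4.3 = 0.6 standard errors.

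**Sensitivity to survey capture**, even spread, s = 0.5, a = 1:

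- p = 0.9: 1 + 0.346 × 0.5 × 0.1/0.9 = 1.02.
- p = 0.5: 1 + 0.346 × 0.5 × 0.5/0.5 = 1.17.

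Real session reactions would come on top of all these figures. They are a true program effect and not an artefact.

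**The case against.** **Sessions are not structured adverse event interviews.** DSMP 5.2.1 illustrates active detection by questions at screening and in surveys, which are alike in both arms, and classes a disclosure over Webex as passive. Protocol 6.2.2 says events are asked about at study visits, but no text calls a group session a visit or describes an event questionnaire there. What facilitators watch for is distress during session activities, which is largely real reaction. This stands. A reader might count nine sessions plus two surveys against two surveys and infer a 5.5-fold difference in detection (11/2). The documents do not support that, because a session and a survey are not comparable detection points.

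**The staff-observation route is restricted.** DSMP section 6 lists "From observations by project staff during baseline screening calls, interventions, and other interactions with participants", but its lead-in reads: "Serious or possibly related adverse events and unanticipated problems can be learned about in the following ways". That route does not cover mild, unrelated events. This also stands. The point rests instead on section 3.3.3, the Schedule of Activities and DSMP 6.2, which carry no such limit.

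**A split may already exist.** The steps for documenting session events are in the manual of operations, which is not available, and DSMP 7.5 is only an outline. So the claim must be that no split is written in these documents, not that none is made.

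**The secondary-outcome link is thin.** A reader might infer from Table 3, where the adverse event row falls under secondary outcomes, that section 5.8 will test adverse events by arm. That rests on table layout alone: the stated aims name opioid use and other HEAL-recommended outcomes, and 5.8 is silent on adverse events.

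**A like-for-like source already exists.** The checklist is identical in both arms. This is true, and it is why the fix is cheap, but the plan does not name it as the comparison.

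**Conclusion.** The point holds and is minor. Followed as written, the plan yields an all-source, by-arm count of non-serious events in which detection favors a higher figure in RAMP, and in which real session reactions cannot be separated from it.

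The size cannot be known from the documents. With equal true rates, 70% survey capture, session capture of 10–50% and attendance of 6/9 to 9/9, the ratio is about 1.01 to 1.07 if events are spread evenly. It reaches 1.21 only if every event falls in the nine weeks, which is unlikely for symptoms that the DSMP describes as fluctuating.

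A reader might infer a large false safety signal. With 50% survey capture, 50% session capture, full attendance and all events open to session detection, the ratio is 1 + 0.5 × 0.5/0.5 = 1.50 (37.5% against 25%). That applies session detection to events throughout six months, whereas the sessions cover nine weeks. Nothing in the documents supports it.

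Nor does the point extend to the efficacy results or to the serious-event questions. The primary analysis uses survey-based pain interference, and hospital stay, disability and life-threatening events are asked of both arms in the same surveys. The halting rules (DSMP 6.4) set no numerical adverse event threshold that a small artefact could trip.

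**What to change.** - **DSMP 7.5** (and section 5.8, if adverse events are to be compared by arm): state that the between-group comparison of non-serious events uses the common survey checklist, as the proportion of participants ever reporting each symptom by 6 months. A participant who ticks an item at either survey counts once.
- **Adverse event record:** add a source field (session, survey, spontaneous, other). If the manual of operations already has one, say so in 7.5.
- **Closed report:** list session-detected non-serious events separately for RAMP, so that real reactions stay visible.
- **Unchanged:** the all-source by-group tables of serious adverse events, deaths and unanticipated problems. No event stops being recorded or reported.

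The cost is about two sentences, one data field and one table; the survey comparison needs no new data. The source field is easiest to set before trial events accumulate. The downside is that the survey comparison omits non-serious events in survey non-responders, for whom section 5.8 allows up to 20% attrition. Any such events known to the team remain in the all-source tables.
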